# 15.19 Assessment of compliance

Compliance will be monitored via pill counting and checking returned empty bottles during study visits. Missed pills will be documented in CRF. Investigators will reiterate dosing schedule and the importance of compliance for efficacy. Participants are considered lost to follow up if there is no end of study visit at post treatment week 12+4 weeks.

There is no provision for supplying additional IMPs which are lost or damaged during the trial. Participants should continue on the study but doses missed due to insufficient drug supply should be recorded as missed doses. Investigators can dispense the next due prescription early to cover for lost or damaged medication. According to local pharmacy policy, if surplus/ replacement medication is available (for example if another patient withdraws from treatment), this can be supplied as IMP for a study participant, provided the medication has not been dispensed from pharmacy, and the usual storage and packaging requirements are complied with.

Any study IMP which is dispensed and unused by the participant will be recalled and destroyed in the site pharmacy. For participants who withdraw during study treatment, they may be eligible to continue treatment on the NHS programme according to their usual clinician's judgement and local Trust guidelines.

# 15.20 Name and description of each Non-Investigational Medicinal Product (NIMP)

There are no Non-IMPs which need to be supplied together with the IMP. Medications required for the management of IMP adverse events or concurrent medical conditions are permitted. Investigators are responsible for checking contraindications and drug-drug interactions.

# 15.21 Arrangements for post-trial access to IMP and care

At the end of study participants will be returned to their usual health care practitioner. This includes participants who fail to achieve SVR12 after completing the study IMP. There is currently no established re-treatment options for study participants or for patients treated with standard of care.

# **16 Equipment and Devices**

No medical device is under investigation for the study.

List of medical equipment required for the study but not under investigation:

- phlebotomy kit
- urinary pregnancy test (beta hCG)

These will be standard NHS kit and will be maintained according to site guideline or usual practice.

# 17 Pharmacovigilance

# 17.1 General Definitions

Term	Definition		
Adverse Event (AE)	Any untoward medical occurrence in a participant to whom a medicinal product has been administered, including occurrences which are not necessarily caused by or related to that product.		
Adverse Reaction (AR)	An untoward and unintended response in a participant to an investigational medicinal product which is related to any dose administered to that participant.  The phrase "response to an investigational medicinal product" means that a causal relationship between a trial medication and an AE is at least a reasonable possibility, i.e. the relationship cannot be ruled out.  All cases judged by either the reporting medically qualified professional or the Sponsor as having a reasonable suspected causal relationship to the trial medication qualify as adverse reactions.		
Serious Adverse Event (SAE)	
 
A serious adverse event is any untoward medical occurrence that:
 
Results in death.
 
Is life-threatening.
 
Requires inpatient hospitalisation or prolongation of existing hospitalisation
 
Results in persistent or significant disability/incapacity.
 
Consists of a congenital anomaly or birth defect.
 
		
	Other 'important medical events' may also be considered serious if they jeopardise the participant or require an intervention to prevent one of the above consequences.  NOTE: The term "life-threatening" in the definition of "serious" refers to an event in which the participant was at risk of death at the time of the event; it does not refer to an event which hypothetically might have caused death if it were more severe.		
Serious Adverse Reaction (SAR)	An adverse event that is both serious and, in the opinion of the reporting Investigator, believed with reasonable probability to be due to one of the trial treatments, based on the information provided.		
Suspected Unexpected Serious Adverse Reaction (SUSAR)	
 
A serious adverse reaction, the nature and severity of which is not consistent with the information about the medicinal product in question set out in the Reference Safety Information (RSI):         
 
In the case of a product with a marketing authorisation, in the summary of product characteristics (SmPC) for that product.
 
In the case of any other investigational medicinal product, in the investigator's brochure (IB) relating to the trial in question.
 
 
 
		

#### 17.2 Site Investigators Assessment

The Principal Investigator is responsible for the care of the participant, or in his/her absence an authorised medic within the research team is responsible for assessment of any event for:

#### Seriousness

Assessing whether the event is serious according to the definitions given in section 17.1.

#### Causality

Assessing the causality of all serious adverse events/reactions in relation to the trial treatment according to the definition given. If the SAE is assessed as having a reasonable causal relationship, then it is defined as a SAR.

#### Expectedness

Assessing the expectedness of all SARs according to the definition given. If the SAR is unexpected, then it is a SUSAR.

#### Severity

Assessing the severity of the event according to the following terms and assessments. The intensity of an event should not be confused with the term "serious" which is a regulatory definition based on patient/event outcome criteria.

- o Mild: Some discomfort noted but without disruption of daily life
- o **Moderate**: Discomfort enough to affect/reduce normal activity
- o Severe: Complete inability to perform daily activities and lead a normal life

#### 17.3 Reference Safety information

Reference Safety Information (RSI) is the information used for assessing whether an adverse reaction is expected.

Please refer to the following SmPC:

Epclusa 400mg/100mg film coated tablets – last updated 13/7/2016 (Gilead Sciences)

# 17.4 Notification and reporting Adverse Events or Reactions

If the AE is not defined as SERIOUS, the AE is documented in the participant's medical notes and CRF and the participant is followed up by the research team.

Recording of AEs should start from the first day of randomisation, to the post treatment 12 week visit. Since participants have commenced treatment on standard NHS care at the time of enrolment, events which occurred prior to enrolment are retrospectively documented.

Serious adverse events which occur during IMP use (i.e. treatment week 13 to 24) and until end of trial (post-treatment week 12) need to be reported. SAEs occurring during treatment but prior to IMP use need to be recorded in medical notes and CRF, but not reported.

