#### Investigational Medicinal Product (IMP)

The study involves 2 drug compounds - sofosbuvir 400mg and velpatasvir 100mg, available as a fixed-dose combination single tablet, marketed under the brand name 'Epclusa'. The IMP is taken orally once per day for 12 weeks, in addition to standard 12 weeks of sofosbuvir/velpatasvir (total 24 weeks treatment).

The recommended treatment for all genotypes of HCV according to EU license is as follows:

- patients without cirrhosis and with compensated cirrhosis Epclusa (sofosbuvir/velpatasvir 400/100mg) for 12 weeks; addition of ribavirin may be considered for genotype 3 infected patients with compensated cirrhosis
- patients with decompensated cirrhosis Epclusa + ribavirin for 12 weeks

Patients co-infected with human immunodeficiency virus (HIV) and patients with recurrent HCV post-liver transplant follow the same recommendation.

Mechanism of action: Velpatasvir is an inhibitor of the HCV non-structural (NS) 5A protein, which exerts activity across all genotypes (1-6) of HCV. Sofosbuvir is an inhibitor of the HCV NS5B RNA polymerase. Both proteins are essential for HCV replication.

Safety: The safety profile of Epclusa is based on pooled data in 1035 patients from Phase 3 clinical studies of patients with or without compensated cirrhosis, who received 12 weeks of sofosbuvir/velpatasvir. The most frequently reported adverse reactions were headache (29%), fatigue (25%) and nausea (14%). These and other adverse events were reported at a similar frequency in placebo treated patients. The proportion of patients who discontinued treatment due to adverse events was 0.2% and the proportion of patients who experienced severe adverse events was 3.2%. [8]

The safety profile of sofosbuvir/velpatasvir (with and without ribavirin) in Child Pugh B decompensated cirrhosis has been evaluated in one open-label study of 267 patients, including 90 patients who received 24 weeks of sofosbuvir/velpatasvir (without ribavirin). Observed adverse events were consistent with the expected clinical sequelae of decompensated liver disease, or the known toxicity profile of ribavirin. Anaemia occurred in 3-4% in patients using 12-24 weeks of sofosbuvir/velpatasvir, which increased significantly to 31% with addition of ribavirin [16].

For further information on the clinical pharmacology, virology, safety and efficacy of sofosbuvir + velpatasvir, please refer to the Summary of Product Characteristics.

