13.8 Trial Schedule

13.8.1 Schedule of Treatment for each visit

13.8.2 Schedule of Assessment (in Diagramatic Format)

Study Visits Schedule for Arm A – 12 weeks of sofosbuvir/velpatasvir							
	Treatment week	0-8	8-12	12	16	20	24
	Visit windows			+/- 7 days	+/- 14 days	+/- 14 days	+ 28 days
Assessments		Pre-	Screening/	End of	Post	Post	End of
		enrolment	baseline	treatment	treatment	treatment	study
NHS treatment visits		х					
Informed consent			х				
Review inclusion/exclusions	Supply participant card		х				
Randomisation			х				
Pregnancy test (if applicable)	Urine test		х				
Document contraception/ breastfeeding advice (if applicable)			х	х	х		
Record demographics			х				
History			х				
Physical examination	Cardiovascular		Х				
	Respiratory		X				
	Gastrointestinal		X				
Review concomitant medications			X	х			
Prescription and dispensing of NHS treatment		х					
Prescription and dispensing study drugs							
Drug accountability	Record missed doses		х	х			
Adverse events recording	Events since week 0		х				
C	Events since last visit			x	x	x	x
Laboratory samples	FBC			Х	Х	Х	Х
	Urea & electrolytes,			Х	Х	X	Х
	creatinine			Х	Х	X	X
	LFTs			Х	Х	X	X
	Albumin			Х	x	x	X
	HCV RNA			Х	(optional)	(optional)	Х
Quality of life questionnaire				x			x

Study Visits Schedule for Arm B – 24 weeks of sofosbuvir/velpatasvir							
	Treatment week	0-8	8-12	12	16	20	24
	Visit windows			+/- 7 days	+/- 7 days	+/- 7 days	+/- 7 days
Assessments		Pre-	Screening/	Study	Study	Study	End of
		enrolment	baseline	treatment	treatment	treatment	treatment
NHS treatment visits		х					
Informed consent			х				
Review inclusion/exclusions	Supply participant card		х				
Randomisation			х				
Pregnancy test (if applicable)	Urine test		х				
Document contraception/			х	х	х	X	Х
breastfeeding advice (if applicable)							
Record demographics			х				
History			х				
Physical examination	Cardiovascular		X				
	Respiratory		X				
	Gastrointestinal		X				
Review concomitant medications			X	х	X	X	X
Prescription and dispensing of NHS		x					
treatment							
Prescription and dispensing study				Х	Х	X	Х
drugs							
Drug accountability	Record missed doses		х	х	Х	X	Х
Adverse events recording	Events since week 0		x				
	Events since last visit			х	х	х	х
Laboratory samples	FBC			X	X	X	X
	Urea & electrolytes,			Х	Х	X	Х
	creatinine			X	Х	X	Х
	LFTs			X	Х	X	Х
	Albumin			x	x	x	Х
	HCV RNA			(optional)	(optional)	(optional)	х
Quality of life questionnaire							X

	Treatment week	28	32	36

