#### Treatment week 12, 16, 20 (study window +/- 7 days) – for arm B (24 weeks)

Record the following between previous visit and this visit:

- Concomitant medications review
- Any adverse events/ serious adverse events
- Any treatment discontinuation (of Sofosbuvir/velpatasvir)
- Any missed doses of treatment reported investigators will perform pill count and review returned empty bottles

Perform blood samples - FBC, U&Es, creatinine, LFTs, albumin. HCV viral load is optional – record if available

Document contraception advice and currently used method (if applicable).

Dispense study medication

- Drugs are prescribed and dispensed every 28 days
- Record batch or lot number, expiry date of dispensed drugs, and date of dispensing
- review administration instructions with participant

Participants who have lost or insufficient medication, at the discretion of their investigator, can have the next due prescription dispensed early. Missing doses should be recorded. (see section 15.19 on assessment of compliance).

Other procedures or examination performed, as deemed appropriate by investigator, should be recorded in medical notes.

Treatment week 24 (study window +/- 7 days) – for arm B (24 weeks) – end of treatment

Record the following between screening visit and end of treatment:

- Concomitant medications review
- Any adverse events/ serious adverse events
- Any treatment discontinuation (of Sofosbuvir/velpatasvir)
- Any missed doses of treatment reported investigators will perform pill count and review returned empty bottles

If participants have left over medication, at the discretion of the study doctor they can complete the remainder tablets, but the end of treatment visit must take place within 7 days of completing medication.

Perform blood samples - FBC, U&Es, creatinine, LFTs, albumin, HCV viral load

Document contraception advice and currently used method (if applicable).

Obtain quality of life questionnaire (SF36) at end of treatment – this does not have to be at the same time as the other visit procedures as long as it is obtained within the visit window

Other procedures or examination performed, as deemed appropriate by investigator, should be recorded in medical notes.

Post-treatment follow up - treatment week 16 & 20 (+/-14 days) for arm A (12 weeks) or treatment week 28 & 32 (+/-14 days) for arm B (24 weeks)

Record the following since the last study visit

• Any serious adverse events

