Perform blood samples - FBC, U&Es, creatinine, LFTs, albumin, optional HCV viral load

Document contraception advice and currently used method (if applicable) – required up to 30 days after last dose of study drug.

Other procedures or examination performed, as deemed appropriate by investigator, should be recorded in medical notes.

End of study - treatment week 24 (+ 28 days) for arm A (12 weeks) or treatment week 36 (+ 28 days) for arm B (24 weeks)

Record the following since the last study visit

Any serious adverse events

Perform blood samples - FBC, U&Es, creatinine, LFTs, albumin, HCV viral load

Obtain quality of life questionnaire (SF36) at end of treatment – this does not have to be at the same time as the other visit procedures as long as it is obtained within the visit window

Other procedures or examination performed, as deemed appropriate by investigator, should be recorded in medical notes.

Study team notifies participant's usual clinician that participant has reached trial endpoints, and returns them to the usual care pathway.

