# 17.5 Notification of AEs of special interest

Adverse events relating to hepatic decompensation (i.e. development of ascites, encephalopathy, variceal bleeding) are of special interest. These events are expected from the natural progression of the underlying condition being treated, but are of particular relevance in patients with compensated or decompensated cirrhosis, due to reports of decompensation in patients with advanced liver disease treated with DAA therapies.

In addition, cardiac arrhythmias in particular severe bradycardia and heart block have been observed with sofosbuvir when used with concomitant medications which lower heart rate (note amiodarone is prohibited).

Therefore the occurrence of the above adverse events, if graded as serious, should be reported according to the procedures detailed in the section 'Notification and reporting for SAE/SUSAR'. AESIs which are not graded as serious are recorded as for other AEs and do not require reporting.

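### The post-treatment visit instructions in 13.8.3 list only serious adverse events, against 17.4 and the schedule, so non-serious events in weeks 13–24 could be captured in Arm B but not in Arm A

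*Protocol*

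**What the plan says.** Three parts of the protocol state what is recorded, and they do not agree.

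- **Section 17.4** sets the general rule: "Recording of AEs should start from the first day of randomisation, to the post treatment 12 week visit". On non-serious events it adds: "If the AE is not defined as SERIOUS, the AE is documented in the participant's medical notes and CRF". Neither sentence is limited to one arm or to the time on treatment.
- **The schedule tables in 13.8.2** have an adverse event row, "Events since last visit". It is marked at weeks 12, 16, 20 and 24 in Arm A, and at weeks 12, 16, 20, 24, 28, 32 and 36 in Arm B.
- **The visit instructions in 13.8.3** differ by treatment phase. On-treatment and end-of-treatment visits ask for "Any adverse events/ serious adverse events". The post-treatment visits (Arm A weeks 16 and 20, Arm B weeks 28 and 32) and the end-of-study visit (Arm A week 24, Arm B week 36) ask for "Any serious adverse events".

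Section 17.5 names hepatic decompensation as being of special interest and says: "AESIs which are not graded as serious are recorded as for other AEs and do not require reporting". Non-serious decompensation events therefore depend on ordinary adverse event recording.

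**The concern.** Weeks 13–24 are where the randomised arms differ: Arm B takes the extension and Arm A takes nothing. Arm A in those weeks is the only concurrent control for the extension. If non-serious events are collected in one arm and not in the other, the extension will appear to cause events that the control arm may have had equally often.

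Safety and tolerability is a secondary objective (11.2), and the proposed-study text in 9.1 speculates that the gain in response will justify any added side effects. Non-serious events also feed the annual risk–benefit assessment (18.0) and the safety review by the Trial Steering Committee (28.0). Events not asked about at the visit may not be recoverable later.

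**Working it through.** **Step 1. The instructions side by side.**

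| Treatment week | Arm A under 13.8.3 | Arm B under 13.8.3 | 17.4 and schedule |
|---|---|---|---|
| 12 | End of treatment: all events | On treatment: all events | All events, both arms |
| 16, 20 | Post-treatment: serious events | On treatment: all events | All events, both arms |
| 24 | End of study: serious events | End of treatment: all events | All events, both arms |
| 28, 32 | Study finished | Post-treatment: serious events | All events, Arm B |
| 36 | Study finished | End of study: serious events | All events, Arm B |

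The 13.8.3 wording follows treatment phase. At weeks 16, 20 and 24 the arms are in different phases, so a split by phase becomes a split by arm.

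**Step 2. Which analyses can be touched.** Sections 11.3.2 and 19.6 name treatment discontinuation, serious adverse events and SF36 scores; 11.4 lists no exploratory endpoints. Serious events are listed at every visit in both arms, and discontinuation and SF36 do not use non-serious events. The effect on the named endpoints is nil. What can be touched is a comparison of all adverse events, or of non-serious events of special interest, that includes weeks 13–24.

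**Step 3. Size, as an illustration.** The protocol states no figure to reproduce. Inputs:

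- 30 patients per arm (19.1).
- Headache 29%, fatigue 25% and nausea 14% in 12-week studies (9.1, paragraph on the investigational product).
- From the same paragraph, "These and other adverse events were reported at a similar frequency in placebo treated patients", so untreated patients can be expected to have such events too.

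Assumptions, not taken from the protocol: the same rate r applies in each 12-week block and in both arms, the blocks are independent, the events are all non-serious, and every site follows 13.8.3.

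*Weeks 13–24 alone.* The expected number recorded in Arm B is 30 × r: 30 × 0.29 = 8.7, 30 × 0.25 = 7.5, 30 × 0.14 = 4.2. Arm A records 0. With 0 of 30 in Arm A, an uncorrected chi-square test passes 3.84 once Arm B has four patients with an event:

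- 4 against 0: 60 × (30 × 4)² / (30 × 30 × 4 × 56) = 4.29
- 3 against 0: 60 × (30 × 3)² / (30 × 30 × 3 × 57) = 3.16

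The binomial probability of four or more in Arm B is 62% at r = 0.14, 96% at 0.25 and 99% at 0.29.

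*Weeks 0–24 cumulatively.* Arm A records r. Arm B records 1 − (1 − r)². The chance of p < 0.05 comes from exact enumeration over both binomials.

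| r | Arm A | Arm B | Expected of 30 | p < 0.05, visit text | p < 0.05, equal capture |
|---|---|---|---|---|---|
| 0.14 | 14% | 26% | 4.2 v 7.8 | 21% | 4.9% |
| 0.25 | 25% | 44% | 7.5 v 13.1 | 33% | 5.0% |
| 0.29 | 29% | 50% | 8.7 v 14.9 | 37% | 5.2% |

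*Range.* If a fraction f of Arm A patients is at sites that follow 13.8.3, the number of Arm A patients whose headache in weeks 13–24 goes unrecorded is f × 0.29 × 30. This runs from 0 (f = 0) to 8.7 (f = 1).

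**The case against.** The strongest reply is that nothing planned is biased. Safety is assessed by discontinuation and serious events, with SF36 alongside, and none of these counts non-serious events. That stands. A reader might infer from the arm difference that the trial's tolerability comparison is biased against 24 weeks. The protocol does not support that, because its named comparisons do not use the affected data.

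Second, the visit text never says that non-serious events are to be left out, and 17.4, the section devoted to recording, and the schedule both require them. A site following either would lose nothing. This also stands: loss is conditional on site practice. It does not settle the matter, because 13.8.3 is the visit-by-visit instruction and its two wordings follow treatment phase consistently. Practice that varied between sites would make the adverse event data hard to interpret.

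Third, the split is by phase, Arm B's own follow-up has the same gap, and a comparison restricted to time on treatment is captured alike in both arms. That is correct, but such a comparison is a weak substitute. By 11.6, Arm A has at most 4 weeks on drug after enrolment, against up to 16 in Arm B, and it drops the concurrent control for the extension.

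Fourth, the 29% comes from pooled phase 3 patients with or without compensated cirrhosis over 12 weeks of treatment. Patients here have cirrhosis, some of it decompensated, and have already taken at least 8 weeks. The rate may not carry over, so the figures are illustrative only.

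Finally, the interval for comparing adverse events may be set in a statistical analysis plan that is not shown. Its absence from the protocol is not a criticism.

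**Conclusion.** The contradiction is established from the text: the post-treatment and end-of-study instructions in 13.8.3 ask for less than 17.4 and the schedule require. Where sites follow 13.8.3, non-serious events, including non-serious decompensation, are recorded in Arm B and missed in Arm A over weeks 13–24, and missed in Arm B over weeks 28–36.

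The named endpoints are unaffected. The consequence is limited to comparisons of all events, or of non-serious events of special interest, that cover weeks 13–24, and there the tilt is against 24 weeks. The figure of 8.7 of 30 against 0 of 30 is an upper illustration resting on a 29% background rate and on every site following the visit text; with no site doing so the loss is zero. The point is more than editorial because it determines which data are collected for a stated secondary objective.

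**What to change.** In 13.8.3, change the event line in the post-treatment follow-up and end-of-study instructions, for both arms, to the wording already used for the on-treatment visits, "Any adverse events/ serious adverse events". This brings the section into line with 17.4 and 13.8.2.

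Make any between-arm comparison of all adverse events over the common interval from randomisation to treatment week 24. Cut that interval by date of onset, since the week 24 visit window is +28 days in Arm A and ±7 days in Arm B.

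The cost is a wording change and slightly more adverse event data entry. No visit is added.
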